4.14.1.2 Handling of Dropouts or Missing Data

Missing evaluation results in the biopsy/surgery will be assigned the worst value. Hence, a side with a positive rhPSMA-7.3 (^{18}F) PET will be considered as false positive (i.e. SoT will be set to negative), while a side with negative rhPSMA-7.3 (^{18}F) PET will be a false negative (i.e. SoT set to positive).

The number and percentage of patients with missing data for the biopsy/surgery will be summarized by major reason, as indicated in Section 4.13.

Imputation of missing dates for concomitant medications and procedures is described in Section 4.7, imputation of missing dates for AEs is described in Section 4.15.1.

PAREXEL International

Blue Earth Diagnostics
BED-PSMA-301

Statistical Analysis Plan

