True positives will be all patients with a surgical pathology confirmed positive region and without a false positive region. False Positive patients will be those patients with any rhPSMA-7.3 (¹⁸F) PET positive region with negative surgical pathology or no surgical pathology.

4.14.3.5 NPV of rhPSMA-7.3 (¹⁸F) PET for detecting pelvic LN metastases compared to surgical pathology on a patient level in which a FN patient is defined as having at least one FN region (right or left pelvis), regardless of any coexisting TN findings.

This analysis concerns patients in the EAP with rhPSMA-7.3 (¹⁸F) imaging, where no LN metastases were detected and LN surgical pathology is available.

Regions where rhPSMA-7.3 (¹⁸F) imaging detected positive LN are not part of this by definition of NPV, hence only TN and FN regions will be taken into account.

NPV = TN / (TN + FN)

True negatives will be all patients with a surgical pathology confirmed negative region and without a false negative region. False negative patients will be those patients with any rhPSMA-7.3 (¹⁸F) PET negative region with positive surgical pathology.

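### The secondary NPV leaves out PET-negative men without pathology, although the SAP's missing-data rule makes them false negatives and the mirrored PPV applies that rule

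*SAP*

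**What the plan says.** Three parts of the SAP deal with missing pelvic node pathology.

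- **General rule (4.14.1.2).** "Missing evaluation results in the biopsy/surgery will be assigned the worst value". For a PET-positive side the result "will be considered as false positive (i.e. SoT will be set to negative"). For a PET-negative side it "will be a false negative (i.e. SoT set to positive").
- **PPV, secondary endpoint 4 (4.14.3.4).** A false-positive patient is one with any "PET positive region with negative surgical pathology or no surgical pathology". This agrees with the general rule.
- **NPV, secondary endpoint 5 (4.14.3.5).** The analysis takes EAP men "where no LN metastases were detected and LN surgical pathology is available". A false-negative patient is one with any "PET negative region with positive surgical pathology"; absent pathology is not mentioned. On the other side of the ratio, "True negatives will be all patients with a surgical pathology confirmed negative region and without a false negative region".

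Both endpoints use the EAP, which requires prostatectomy and node dissection but not usable histology (SAP 4.5). The Per Protocol Population (PP) is the subset with histology that allows the standard of truth to be set. SAP 4.13 plans a category for missing hemipelvis results, so the SAP allows for operated men, or sides, without pathology. SAP 4.17, which lists changes to the planned analysis, does not mention a different rule for the NPV.

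**The concern.** Endpoints 4 and 5 are worded as mirror images. A reader will expect missing pathology to count against the tracer in both or in neither. As written, the PPV takes the penalty and the NPV does not.

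The man with pathology on one side only is the least settled case. Suppose one side is confirmed negative and the other is PET-negative without pathology. The true-negative definition asks for one confirmed negative region and no false-negative region, and a false-negative region in 4.14.3.5 needs positive pathology. He can therefore be read as a true negative in the NPV. Under 4.14.1.2 and Table 4b he is a false negative in the sensitivity table. SAP 4.14.3.5 does not say whether pathology must be available per man or per side.

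At stake is whether the two predictive values in one report rest on the same rule, and whether that is fixed in the SAP or left to the programming.

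**Working it through.** **The plan's own figures.** SAP 4.16 assumes 300 evaluable men, 25% pN1, sensitivity 40% and specificity 90%, with 90% power for each co-primary test. Exact binomial tests at one-sided 0.025 reproduce this:

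- Sensitivity against 22.5%: reject at 25 or more of 75; actual alpha 0.0207, power 90.4%.
- Specificity against 82.5%: reject at 197 or more of 225; actual alpha 0.0246, power 90.6%.

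The documents state no expected NPV and no expected number of men without pathology.

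**Expected counts at the design values.**

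- TP = 0.40 × 75 = 30; FN = 75 − 30 = 45
- TN = 0.90 × 225 = 202.5; FP = 225 − 202.5 = 22.5
- PET-negative men = 202.5 + 45 = 247.5
- NPV with complete pathology = 202.5 / 247.5 = 81.8%

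**Men with no pathology on either side.** Let k PET-negative men lack pathology, with the same node status on average as the rest. The values of k are assumptions.

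- Exclusion (4.14.3.5): TN and FN shrink in proportion, so the NPV stays at 81.8%.
- Worst value (4.14.1.2): NPV = 202.5 × (1 − k/247.5) / 247.5
- FN in the NPV: 45 × (1 − k/247.5). FN in the sensitivity table: the same plus k.

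| k | NPV, exclusion | NPV, worst value | FN in NPV | FN in sensitivity table |
|---|---|---|---|---|
| 5 | 81.8% | 80.2% | 44.1 | 49.1 |
| 10 | 81.8% | 78.5% | 43.2 | 53.2 |

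**Men with one side missing.** Suppose the k men are among the 202.5 and have one confirmed negative side. Read as true negatives, they leave the NPV at 81.8%. Counted as false negatives under 4.14.1.2, they give 197.5 / 247.5 = 79.8% (k = 5) or 192.5 / 247.5 = 77.8% (k = 10).

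**The asymmetry with the PPV.** Suppose 5% of all 300 men lacked pathology whatever their PET result. The PPV under 4.14.3.4 would be 30 × 0.95 / 52.5 = 54.3%, against 30 / 52.5 = 57.1% on observed pathology. The NPV under 4.14.3.5 would stay at 81.8%, against 202.5 × 0.95 / 247.5 = 77.7% under the worst-value rule.

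**Is exclusion biased against the truth?** Take k = 10 and let q be the true share of node-positive men among them. The full-cohort NPV is [202.5 × (1 − 10/247.5) + 10 × (1 − q)] / 247.5 = [194.3 + 10 × (1 − q)] / 247.5.

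| q | Full-cohort NPV | Exclusion |
|---|---|---|
| 0 | 82.6% | 81.8% |
| 18.2% (45/247.5) | 81.8% | 81.8% |
| 50% | 80.5% | 81.8% |
| 100% | 78.5% | 81.8% |

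Exclusion is right if the unverified men resemble the verified ones, too low if fewer of them are node-positive, and too high if more are. The worst-value rule matches the truth only at q = 100%.

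**The case against.** The strongest reply is that leaving out unverified men is the usual way to estimate an NPV, and that the gap in the first table measures how pessimistic the worst-value rule is. It treats every unverified PET-negative man as node-positive, where the design values imply 18.2%. This stands. A reader might infer that the NPV is biased upward; the documents do not support that, because nothing in them says why pathology would be missing or in whom.

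A reader might also infer that the NPV and sensitivity tables cannot be reconciled. That goes too far. SAP 4.13 lists each man's region-level and patient-level classification, including those for 4.14.3.4 and 4.14.3.5, and SAP 4.14.1.2 tabulates missing pathology by reason, so most of the gap can be traced. Part of any mismatch is by design: one true-positive region makes a man a true positive in the primary analysis, even if his other side is a false negative.

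Third, the one-side-missing man has another reading. If 4.14.1.2 is applied first, his missing side is a false-negative region and he is not a true negative. That is tenable, but the text does not choose between the readings, and a man with no pathology at all is still excluded.

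Finally, SAP 4.14.1 defines an NPV for each reader without the restriction, so a worst-value NPV may already be planned. If so, two NPVs with different denominators would appear, and the SAP does not say how they relate.

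**Conclusion.** The SAP contradicts itself on one secondary endpoint. The general rule and the PPV agree; the NPV departs from both without saying so. The NPV as written is never less favourable than under the SAP's own rule. The difference is about 1.6 points with 5 unverified PET-negative men and 3.3 points with 10, or 2.0 and 4.0 points if they are one-side-missing men read as true negatives. These sizes rest on the design values and on assumed counts. If all EAP men have usable pathology on both sides, the difference is zero.

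The NPV is descriptive (SAP 4.14.3), and no test or success criterion depends on it. This is a consistency correction that should be made, not a threat to the primary conclusion.

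**What to change.** In SAP 4.14.3.5:

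1. State that 4.14.1.2 applies, side by side, and remove the restriction to men with pathology available.
2. Define a false-negative patient as one with any PET-negative region whose surgical pathology is positive or absent, mirroring 4.14.3.4.
3. State that a true-negative patient needs every PET-negative side confirmed negative.
4. Report PPV and NPV on observed pathology only, in the EAP, as the supportive pair. The PP is not a substitute, because it also removes men with major protocol deviations that affect the scan or the histology.

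The cost is a sentence or two, one programming condition and one supportive table. The reported NPV becomes slightly less favourable. False-negative counts may still differ from the sensitivity table where a man has one true-positive and one false-negative region; a footnote should say so.

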4.14.3.6 Upstaging

- a) The percentage of patients being upstaged to N1 or M1 disease;*
- b) The percentage of patients in whom planned RP is converted to EBRT.*

The endpoints will be calculated as follows:

- Upstaging to N1 = Proportion of patients with positive BIE PET finding by BIE and negative conventional imaging finding from local investigator in pelvic lymph nodes, out of all the patients with evaluable scans.
- Upstaging to M1 = Proportion of patients with positive BIE PET finding and negative conventional imaging finding from local investigator in other (extra-pelvic) areas, out of all the patients with evaluable scans.

PAREXEL International

Blue Earth Diagnostics
BED-PSMA-301

Statistical Analysis Plan

- Planned RP converted to EBRT = Proportion of patients with positive BIE PET finding and planned RP changed to EBRT by local investigator, out of all the patients with evaluable scans.

4.14.3.7 Kappa statistic for the agreement between and within blinded independent readers on the interpretation of rhPSMA-7.3 (¹⁸F) scans.

This analysis concerns all EEP patients.

For this analysis, the patient's categorization to positive or negative by the blinded readers will be used, in pelvic lymph nodes and in extra-pelvic region.

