3.2 Secondary Objectives

The secondary objectives of the study are:

1. To assess the Verified Detection Rate (VDR) for M1 disease of rhPSMA-7.3 (¹⁸F) PET findings (as determined by central BIE) on a patient level in patients with newly diagnosed unfavorable intermediate-, high-, or very high-risk PCa using histopathology or confirmatory imaging.
2. To assess the VDR for M1 disease of rhPSMA-7.3 (¹⁸F) PET findings (as determined by central BIE) on a patient level in patients with negative conventional imaging.
3. To assess the positive predictive value (PPV) of rhPSMA-7.3 (¹⁸F) PET for N1 and M1 lesions (as determined by central BIE) compared to histopathology or confirmatory imaging (M1 lesions only).
4. To assess the PPV of rhPSMA-7.3 (¹⁸F) PET for detecting pelvic LN metastases compared to surgical pathology on a patient level in which a FP patient is defined as having at least one FP region (right or left pelvis), regardless of any coexisting TP findings.
5. To assess the negative predictive value (NPV) of rhPSMA-7.3 (¹⁸F) PET for detecting pelvic LN metastases compared to surgical pathology on a patient level in which a FN patient is defined as having at least one FN region (right or left pelvis), regardless of any coexisting TN findings.
6. To assess the impact of rhPSMA-7.3 (¹⁸F) PET BIE on a) upstaging patients planned for RP or b) converting planned RP to EBRT.
7. To determine the inter- and intra-reader agreement of rhPSMA-7.3 (¹⁸F) scan interpretation by blinded independent readers.
8. To assess the safety of rhPSMA-7.3 (¹⁸F) injection in patients.

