5.2 Secondary Endpoints

The secondary endpoints for this study will be:

1. Percentage of patients in whom rhPSMA-7.3 (¹⁸F) imaging detects at least one verified M1 metastasis, as determined by central BIE.
2. Percentage of patients with negative conventional imaging for M1 disease in whom rhPSMA-7.3 (¹⁸F) PET detects at least one verified M1 metastasis, as determined by central BIE.
3. Patient level PPV of rhPSMA-7.3 (¹⁸F) PET BIE for N1 and M1 lesions compared to histopathology or confirmatory imaging (M1 lesions only).
4. PPV of rhPSMA-7.3 (¹⁸F) PET for detecting pelvic LN metastases compared to surgical pathology on a patient level in which a FP patient is defined as having at least one FP region (right or left pelvis), regardless of any coexisting TP findings.
5. NPV of rhPSMA-7.3 (¹⁸F) PET for detecting pelvic LN metastases compared to surgical pathology on a patient level in which a FN patient is defined as having at least one FN region (right or left pelvis), regardless of any coexisting TN findings.
6. a) The percentage of patients being upstaged to N1 or M1 disease;
b) The percentage of patients in whom planned RP is converted to EBRT.
7. Kappa statistic for the agreement between and within blinded independent readers on the interpretation of rhPSMA-7.3 (¹⁸F) scans.
8. Safety (AEs, vital signs clinical laboratory evaluations, 12-lead ECG and focused physical examinations) of rhPSMA-7.3 (¹⁸F) injection in patients.

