In addition, a 12-lead ECG will be performed pre-IP administration on the day of rhPSMA-7.3 (¹⁸F) injection and at the safety follow-up visit within 1 to 3 days post-IP administration (may occur within 1 to 5 days post-IP administration due to the COVID-19 pandemic).

Any clinically significant changes in vital sign measurements (as determined by the site investigator) should be reported as an AE.

9.1.6 *Diagnostic Imaging*

All patients will receive an IV bolus of rhPSMA-7.3 (¹⁸F) injection and undergo a PET scan as described in the Study Imaging Manual.

For each patient, the PET imaging results will be reported to the responsible physician prior to the planned RP. Within 1 to 3 days post-IP administration, the patient must return to the clinic for safety follow-up (may occur within 1 to 5 days post-IP administration due to the COVID-19 pandemic). Clinical review of imaging results and discussion of further procedures/treatments with the patient should also take place at this visit if feasible. In cases where the rhPSMA-7.3 (¹⁸F) PET imaging results are not available at the safety follow-up visit, imaging results and further procedures/treatment plan should be discussed with the patient within 7 days after rhPSMA-7.3 (¹⁸F) imaging (this may be conducted by telephone at the clinician's discretion).

Within 45 days post-IP administration (may be extended up to 60 days due to the COVID-19 pandemic), the patient will receive treatment:

- Standard of care surgical treatment of PCa, including a PLND; **or**
- If the rhPSMA-7.3 (¹⁸F) PET scan detects M1 lesion(s):
 - A biopsy/surgery and/or additional imaging to confirm M1 lesion(s) will be required prior to initiation of treatment.

Image Interpretation

Results of local rhPSMA-7.3 (¹⁸F) PET interpretation will be used to guide biopsy/confirmatory procedures, if indicated, as well as for the physician to discuss further procedures/treatments with the patient.

For the evaluation of the co-primary endpoints, rhPSMA-7.3 (¹⁸F) PET image data will be appropriately blinded, randomized, and read by 3 trained, independent central PET readers.

9.1.7 *Biopsy/Surgery*

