11.4 Image Transfer

Following the completion of PET imaging at the study site, the scan data will be sent to the Invicro Imaging Core Lab (Invicro, LLC) using either the iPACS software or on physical media by courier. Full details are in the Study Imaging Manual.

11.5 rhPSMA-7.3 (¹⁸F) Image Reads

All local and central readers will undergo training in interpretation of rhPSMA-7 (¹⁸F) PET scans, and will have a training set available for reference. Primary evaluation and reporting of the PET scan will be based on the site-based local read (as per standard of care).

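### Objective 6, endpoint 6b and the SAP formula for RP-to-EBRT conversion do not agree: the formula requires a positive central read, so it can equal or fall below the endpoint and can vary by reader

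*SAP*

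**What the plan says.** The measure is stated in three ways.

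- **Objective 6** (Protocol 3.2, repeated in SAP 2.2) concerns the impact of "PET BIE on a) upstaging patients planned for RP or b) converting planned RP to EBRT". It names the central read.
- **Endpoint 6b** (Protocol 5.2, repeated in SAP 3.2.2 and as item b at the top of SAP 4.14.3.6) is "The percentage of patients in whom planned RP is converted to EBRT". It names no read.
- **The formula** in SAP 4.14.3.6 is "Planned RP converted to EBRT = Proportion of patients with positive BIE PET finding and planned RP changed to EBRT by local investigator", taken "out of all the patients with evaluable scans". It requires both a conversion and a positive central read.

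On who uses which read, Protocol 9.1.6 says that the local "PET interpretation will be used to guide biopsy/confirmatory procedures, if indicated, as well as for the physician to discuss further procedures/treatments with the patient". Protocol 11.5 says "Primary evaluation and reporting of the PET scan will be based on the site-based local read (as per standard of care"). The central read appears in Protocol 9.1.6 in connection with the co-primary endpoints: "image data will be appropriately blinded, randomized, and read by 3 trained, independent central PET readers".

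Protocol 9.1.7 lets a patient with no M1 lesion identified go to EBRT once the PET result is known, if patient and physician prefer it. The rationale goes on the eCRF. No positive finding is required.

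SAP section 1 gives the SAP precedence over the protocol where they differ. SAP 4.17 lists changes to the planned analysis and does not mention this formula.

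**The concern.** A change of planned treatment is one observed fact per patient. The formula filters that fact through a read which, on the documents' account, is not the one that informs the decision. A conversion made on a positive local read drops out if the central reader calls the scan negative. So does a conversion that follows a negative scan, although it meets the endpoint as worded.

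There are two further difficulties. The formula depends on the reader, and the section does not say which reader's value is endpoint 6b. The condition also names no location: the two upstaging bullets above it specify pelvic nodes and extra-pelvic areas, while this bullet just says positive. SAP 4.9 lists prostate as a PET result category, so two programmers could produce different tables from the same data.

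At stake is the reported rate of management change, a secondary descriptive result. Readers would take a figure labelled as conversion from RP to EBRT to be the rate of conversion.

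**Working it through.** The documents give no rate, sample size or power for endpoint 6b, so there is no planned figure to reproduce. The check is set logic followed by an illustration.

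**1. Notation.** Let C be the number of patients whose planned RP is changed to EBRT, N the number with evaluable scans, and q_r the share of the C patients whom reader r calls positive.

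- Endpoint 6b as worded: C / N.
- SAP 4.14.3.6 for reader r: C × q_r / N.
- Difference: C × (1 − q_r) / N, which is never negative and is zero only when q_r = 1.

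The denominator is not the source of the difference. The bullet sets its own, all evaluable scans, and so departs from the EAP default in SAP 4.14.

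**2. Can q_r be below 1 under the plan?** Yes, by two routes. Conversion does not require a positive scan (Protocol 9.1.7). The local and central reads can also disagree: SAP 4.12 (item 3) and 4.14.3.1 both provide for an M1 lesion seen by a blinded reader but not by the site.

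**3. How many values?** SAP 4.9 calls for three runs, one per blinded reader, in describing the primary analysis. SAP 4.14.1 repeats every such analysis for the majority read. A formula containing a BIE result can therefore give up to 3 + 1 = 4 values. They coincide if the readers agree on all converted patients.

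**4. Illustration.** C and q are not in the documents and are assumed. N = 375 is the planned enrollment, used as a stand-in for evaluable scans.

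| C (assumed) | Endpoint C/N | SAP, q = 0.3 | SAP, q = 0.9 | SAP, q = 1 |
|---|---|---|---|---|
| 10 | 10/375 = 2.7% | 3/375 = 0.8% | 9/375 = 2.4% | 2.7% |
| 20 | 20/375 = 5.3% | 6/375 = 1.6% | 18/375 = 4.8% | 5.3% |
| 40 | 40/375 = 10.7% | 12/375 = 3.2% | 36/375 = 9.6% | 10.7% |

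With C = 20 and three readers positive in 40%, 50% and 60% of the converted patients, the same 20 conversions would be reported as 8/375 = 2.1%, 10/375 = 2.7% and 12/375 = 3.2%.

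**5. How easily does a gap arise?** If each of 20 converted patients is independently called positive with probability 0.9, the chance that a given reader misses at least one is 1 − 0.9^20 = 88%.

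**6. Effect of the missing location.** If prostate uptake counts as positive, q may be close to 1 and the condition does little. If only nodal or distant findings count, q could be much lower. The bullet does not decide between these.

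**The case against.** The strongest reply is that the central-read condition was not invented in the SAP. Objective 6 asks about the impact of the central read in the protocol itself, and the SAP formula can be read as carrying that out. This stands. A reader might infer that the SAP quietly departed from the protocol, and the documents do not support that. The protocol's objective and endpoint differ from each other, and the SAP followed the objective.

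A second reply is that an unconditional count may overstate the impact of PET, because a patient may move to EBRT after a negative scan or from preference. This also stands, and some attribution to PET is reasonable. It argues for a breakdown by the read that informed the decision, which is the local one, and for use of the recorded rationale.

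Third, a reader might say that the clinician never sees the BIE. That is an inference. The documents assign reporting and treatment discussion to the local read and nowhere send the central read to the physician, but they do not expressly bar its release.

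Fourth, much of the information appears elsewhere. SAP 4.14.3 summarizes each patient's pathway, and SAP 4.10 summarizes surgery and additional treatment. The conversions may be recoverable from those outputs, but none of them is defined as the 6b rate.

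**Conclusion.** The inconsistency is real and should be resolved. As written, SAP 4.14.3.6 computes a subset of endpoint 6b, selected by a read that the documents do not link to the treatment decision, with positive left undefined.

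The direction is certain only as equal or lower. It is tempting to say that the formula undercounts and gives a different answer for each reader. The documents do not support either as a certainty: the first needs a reader to call at least one converted patient negative, and the second needs readers to differ on converted patients. The size cannot be derived from the documents. The percentages above rest on assumed counts and show the mechanism only; the gap is nil if every converted patient is called positive.

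The endpoint is secondary and descriptive, with no test or success criterion attached. The co-primary tests and the trial's success rule are unaffected.

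**What to change.** 1. In SAP 4.14.3.6, calculate 6b once: all patients with planned RP changed to EBRT after the PET scan, out of all patients with evaluable scans.
2. To show attribution to PET, break the converted patients down by local read result (N1, M1, negative) and by the rationale on the eCRF.
3. Present any cross-tabulation against the BIE as supportive only, and define positive by location, as the two upstaging bullets do.
4. Reconcile part b of objective 6 (Protocol synopsis and 3.2, SAP 2.2) with endpoint 6b, and record the change in SAP 4.17.

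The cost is small: some wording and one table. The change of management and its rationale are already recorded on the eCRF (Protocol 9.1.7), and SAP 4.9 already lists the local reads, so no new data are needed.
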